### 3.A NUMBER OF PATIENTS / ENROLMENT/ FOLLOW-UP PERIOD

This study will include a total of 306 patients (*153 in each group, see section 7.B.2*), randomly assigned to one of the two study groups detailed in section 4.A by centre, smoking status and need for respiratory assistance (*i.e., home oxygen therapy or Non-Invasive Ventilation*) for chronic respiratory failure at Selection.

The planned total study duration is 52 months, including a 38-month enrolment period and a 14-month follow-up for each randomised patient.

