## **VISITS AT THE INVESTIGATIONAL CENTRE (*VISITS 2 TO 5*)**

**Visits 2 to 5** are scheduled at Month 3, Month 6, Month 9 and Month 12 from Visit 1, respectively. These visits may vary from their planned timelines starting at Visit 1 by  $\pm 30$  days, without modifying the initially planned timelines of the following visits if a given visit needs to be advanced or postponed.

**During Visits 2 to 5**, the investigator will record the following data in the e-CRF:

- Date of Visit,
- Results of the physical examination including vital signs (*i.e.*, *systolic and diastolic blood pressures*), weight and pulse oximetry (*pulse rate and SpO2*) on room air and also on oxygen for patients on oxygen therapy,
- Changes in social conditions, if applicable,
- Changes in smoking status, if applicable,
- Recovery from concomitant diseases since the last visit, if applicable,
- Changes in COPD and non-COPD medication, including oxygen therapy, CPAP, Non-Invasive Ventilation and vaccines (*as detailed in section 5.D*), since the last visit, if applicable,
- Occurrence of COPD exacerbations (*as defined in section 6.A.2.2*) since the last visit,
- Occurrence of other Adverse Events (*see section 6.B*) since the last visit,
- For patients on oxygen therapy, checking of the *NOWOX* device (*to detect the need for an exchange or return of the device at study end*), and, if applicable, the reason for exchanging or returning the *NOWOX* device and the serial number of the new *NOWOX* device assigned, whenever necessary; of note, patients starting oxygen therapy during their study participation will be given a *NOWOX* following the procedure described in section 4.B.3.1 and their start date and criteria for oxygen prescription will be collected, as described in section 4.B.1.2.
- Use of health care services (*see section 6.A.2.3*) since the last visit.

**At Visit 3 (Month 6) and Visit 5 (Month 12 or study end in case of premature withdrawal)**, additional questionnaires and examinations will be performed as follows:

- The SGRQ-C, 15D and HADS questionnaires (*as detailed in sections 6.A.2.4 and 6.A.2.7 and provided in Appendix 3*), self-administered before the consultation with the investigator at **Visit 3 (M6)** and **Visit 5 (M12)**,
- Assessment of the severity of dyspnoea using the modified Medical Research Council Dyspnoea Scale at **Visit 5 (M12)**,
- Comorbidities to allow the calculation of the Charlson Comorbidity Index at **Visit 5 (M12)**,

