#### 6.A.2.8. Compliance to oxygen therapy

Compliance to oxygen therapy will be assessed for each randomised patient being on oxygen therapy at Selection or during his/her study participation using the data stored and downloaded from the *NOWOX* device.

These data will be used to estimate the average daily use of oxygen therapy of each randomised patient being on oxygen therapy during the time period he/she is on oxygen therapy during the *Follow-Up Period*, in hours per day.

Average daily use of oxygen therapy will be calculated from all cumulated percentages of oxygen use per hour recorded by the *NOWOX* device throughout the *Follow-Up Period*, converted to hours and normalised by using the total number of days of the patient's effective follow-up at home (*days during which patient is hospitalised will not be taken into account for the calculation*).

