In the subgroup of patients on oxygen therapy at Selection and/or during their study participation and on the period of their oxygen prescription overlapping their holding of the *NOWOX* device, the average daily duration prescribed will be tabulated by study group. For each patient for whom a change in the daily duration of oxygen prescription is recorded throughout the *Follow-Up Period*, the individual daily duration of oxygen prescription will be estimated by using the sum of all recorded daily durations prescribed multiplied by the number of days of the corresponding prescription, divided by the total number of days on oxygen therapy. In case of missing or incomplete information necessitating monthly approximation in this average calculation, it will be considered that each month lasts 30.5 days.

**Compliance to oxygen therapy:** in the subgroup of patients on oxygen therapy at Selection and/or during their study participation and on the period of their oxygen prescription overlapping their holding of the *NOWOX* device, the average daily use of oxygen therapy over 24 hours, as well as the average use of oxygen therapy at night (*i.e., over the time interval [22:00 ; 6:00]*) and the average use of oxygen therapy during the day (*i.e., over the time interval [06:00 ; 22:00]*) will be calculated separately over at most eight (8) successive periods (*for the first patients included in the study who have been followed up 24 months*) defined by the scheduled visits of the patients at the investigational centre, without taking into account the recordings collected by the *NOWOX* device on the day of each actual visit, *i.e.,* when applicable, over the successive periods:

- between the day following the actual date of Visit 1 and the day preceding the actual date of Visit 2 (*both included*) (*period 1*),
- between the day following the actual date of Visit 2 and the day preceding the actual date of Visit 3 (*both included*) (*period 2*),
- ... and so on, up to the last period between the day following the actual date of Visit 8 and the day preceding the actual date of Visit 9 (*both included*) (*period 8, if applicable*).

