The average daily use of oxygen therapy and its two (2) components at night and during the day separately, will be tabulated by study group, over each period separately, using quantitative descriptive statistics. These tabulations, as well as their graphical representations and analyses over time described below will be performed twice in the subgroup of patients on oxygen therapy at any time throughout their study participation and on the period of their oxygen prescription overlapping their holding of the *NOWOX* device: first, on all recordings collected by the *NOWOX* device for all patients constituting the ITT data set, and second, on the recordings collected on the days when patients from the ITT data set are not on any concomitant respiratory assistance (*i.e. Continuous Positive Airway Pressure (CPAP) therapy and/or home Non-Invasive Ventilation (NIV)*) as reported by the investigators. They will be repeated in a second step in the subgroup of patients on continuous LTOT (*i.e., with daily oxygen duration prescribed of 15 hours or more*) at any time throughout their study participation and on the period of their LTOT prescription overlapping their holding of the *NOWOX* device.

Moreover, to visualise the evolution of the recordings, arithmetic means of each average daily use of oxygen therapy calculated separately and their 95.0% confidence intervals will be represented graphically (*the x-axis being the period-axis and the y-axis being the arithmetic mean-axis*) with both study groups being represented separately on the same graph.

An analysis over time of the mean profile of the average daily use of oxygen therapy and its two (2) components separately will be performed within a mixed model to deal with patients followed-up over different duration, using the MIXED procedure of the current version of the SAS® software and type III sums of squares. The global parametric analysis of variance model on repeated measurements used will include the following factors:

- study group and period of evaluation as fixed factors,
- interaction between the study group and the period of evaluation as fixed factor,
- patient as random factor.

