In a first step, the best structure of the variance-covariance matrix will be identified using the Akaike's Information Criterion (AIC), which is based on the Restricted Maximum Likelihood (REML) and the number of variance parameters. The model with the AIC lowest value will be considered as the best one. In a second step, inference will be drawn about fixed effects in the frame of the model with the best structure of the variance-covariance matrix selected in the first step.

When relevant, appropriate contrasts will be calculated and the associated confidence intervals will be displayed. In case of a statistically significant interaction evidenced at level  $\alpha = 0.10$ , further separate parametric analyses of variance may be carried out, if appropriate and potentially relevant from a clinical point of view.

Moreover, to explore further the collected data, the average daily use of oxygen therapy and its two (2) components separately will be calculated separately over the first week (*i.e., the first 7 days*) following each patient's visit at the investigational centre (*from the day following the actual date of Visit 1 onwards*) and over the last week (*i.e., the last 7 days*) preceding each patient's visit at the investigational centre (*from the last 7 days preceding the actual date of Visit 2 onwards*), without taking into account the recordings collected by the *NOWOX* device on the day of each actual visit. These weekly means will be tabulated by study group, over each 7-day period separately, using quantitative descriptive statistics. The pre-investigational centre visit weekly means and the post-investigational centre visit weekly means separately will be represented graphically and analysed in the same way as the quarterly means of the daily use of oxygen therapy previously described.

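### Oxygen compliance is tested between arms in patients who can enter the subgroup after randomisation; the test belongs in patients on oxygen at Selection

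*Protocol*

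**What the plan says.** **Population.** Section 6.A.2.8 sets the criterion: "Compliance to oxygen therapy will be assessed for each randomised patient being on oxygen therapy at Selection or during his/her study participation". Section 7.B.3.5 carries this through. Hours per day are tabulated, plotted and modelled "in the subgroup of patients on oxygen therapy at any time throughout their study participation". The differences between recorded use and prescribed duration are calculated on the same basis: "In the subgroup of patients on oxygen therapy at Selection and/or during their study participation". For LTOT, "They will be repeated in a second step in the subgroup of patients on continuous LTOT", and that subgroup too can be joined at any time during participation.

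**Late entry in practice.** Under Visits 2 to 5 (section 4.B.3.2), "patients starting oxygen therapy during their study participation will be given a" *NOWOX* device, so they supply data from then on.

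**Model.** The terms are "study group and period of evaluation as fixed factors", their interaction, and patient as random factor. Nothing represents oxygen status at Selection or prescribed hours. The analysis goes beyond description: "inference will be drawn about fixed effects in the frame of the model", contrasts and confidence intervals follow, and an interaction significant at 0.10 may lead to further separate analyses.

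**Status.** Section 7.B declares everything other than the primary analysis exploratory and descriptive, and rules out causal interpretation.

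**The concern.** Randomisation takes place at Visit 0. A subgroup fixed by then is balanced between arms in expectation. A subgroup that is also filled by later events keeps that property only if those events are unrelated to arm.

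Here they could be related. Oxygen is prescribed at the investigator's discretion (section 5.A.3), and centre staff know the allocation (section 4.B.2). Only the Intervention arm has weekly symptom reports, home SpO2 measurement when status worsens, and alarms to the investigator, for whom a therapeutic adjustment is a listed response (section 5.A.1.2, Appendix 2). The protocol itself allows that oxygen onset may differ by arm: section 7.B.3.5 tabulates it by study group and, if relevant, applies a log-rank test.

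If the arms differ in how many patients start oxygen, or in which patients start, the compliance contrast mixes the programme's effect on adherence with its effect on who is in the comparison. Later starters contribute only to later periods, so the mix can also change over time by arm and enter the group-by-period interaction. Section 1.C singles out LTOT compliance as a likely route of benefit, so readers will look at this result.

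**Working it through.** **Inputs.** The protocol states no oxygen prevalence, start rate, daily hours or expected compliance effect, so there is no planned figure to reproduce for this analysis. The only design input used is 153 patients per arm (section 7.B.2: 143/(1 − 0.0625) = 152.5, rounded up). Everything else below is an assumption, and the true effect on compliance is set to zero throughout.

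**Formula.** Let p be the proportion on oxygen at Selection and r the proportion of the others who start later.

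- Share of later starters in an arm's subgroup: f = (1 − p)r / [p + (1 − p)r].
- If later starters use g h/day less than patients on oxygen at Selection, the spurious difference is d = −g(f_I − f_C), with I for Intervention and C for Control.

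**Illustration 1, moderate.** p = 0.60, 14 h/day in patients on oxygen at Selection, r = 0.10 in Control.

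- Starters at 10 h/day, r = 0.20 in Intervention. Control: (0.60×14 + 0.04×10)/0.64 = 13.75 h. Intervention: (0.60×14 + 0.08×10)/0.68 = 13.53 h. Difference −0.22 h/day.
- Starters at 12 h/day, r = 0.15 in Intervention. Control: (8.4 + 0.04×12)/0.64 = 13.875 h. Intervention: (8.4 + 0.06×12)/0.66 = 13.82 h. Difference −0.06 h/day.

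**Illustration 2, wider range.** SD 5 h/day; SE = 5√(1/n_I + 1/n_C); two-sided rejection rate = Φ(|d|/SE − 1.96) + Φ(−|d|/SE − 1.96).

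| p | r, I vs C | g (h) | f, I vs C | d (h/day) | n, I vs C | Rejection |
|---|---|---|---|---|---|---|
| 0.6 | 0.10 vs 0.10 | 2 to 6 | 0.063 vs 0.063 | 0 | 98 vs 98 | 5.0% |
| 0.6 | 0.20 vs 0.10 | 2 | 0.118 vs 0.063 | −0.11 | 104 vs 98 | 5.3% |
| 0.6 | 0.20 vs 0.10 | 4 | 0.118 vs 0.063 | −0.22 | 104 vs 98 | 6.1% |
| 0.4 | 0.20 vs 0.10 | 4 | 0.231 vs 0.130 | −0.40 | 80 vs 70 | 7.8% |
| 0.4 | 0.30 vs 0.10 | 6 | 0.310 vs 0.130 | −1.08 | 89 vs 70 | 27.2% |

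**Illustration 3, what use minus prescription corrects.** p = 0.50, everyone takes 80% of the prescribed time, with 16 h prescribed to patients on oxygen at Selection and 10 h to later starters.

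- r = 0.10: f = 0.05/0.55 = 0.091; mean prescribed 15.45 h; use 12.36 h; absolute difference −3.09 h; relative difference −20%.
- r = 0.30: f = 0.15/0.65 = 0.231; mean prescribed 14.62 h; use 11.69 h; absolute difference −2.92 h; relative difference −20%.

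Raw hours fall by 0.67 h/day with unchanged adherence. The absolute difference moves by 0.17 h and the relative difference not at all.

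That protection depends on later starters adhering as well as the others. If they do not, the shift in relative compliance is (their relative compliance minus that of the others) × (0.231 − 0.091), or 0.14 percentage point for every percentage point of discrepancy.

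**Equal numbers, different patients.** Equal start rates are not sufficient. With p = 0.6 and r = 0.10 in both arms (f = 0.0625), each 1 h/day by which starters' usual use differs between arms gives 0.06 h/day of spurious difference.

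**Baseline subgroup.** Restricted to patients on oxygen at Selection, f = 0 in both arms and this mechanism contributes nothing.

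**The case against.** The other side has a good deal of substance.

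- **Prescribing is handled separately.** A reader might infer that differences in prescribing would simply be read as differences in compliance. The documents do not support that. Section 7.B.3.5 tabulates prescribed duration by arm and models use minus prescription, in absolute and relative terms. Illustration 3 shows that this removes most of the effect of prescribed hours. Selection by who starts oxygen remains, because the population is the same.
- **An imbalance would be visible.** New oxygen starts, their timing and their criteria are tabulated by arm, with a repeat for LTOT if relevant. This stands, but it reveals a problem without supplying an unaffected comparison.
- **No causal claim is planned.** Section 7.B says so. The model still yields between-arm tests and intervals, but no confirmatory conclusion rests on them.
- **The arms may well stay comparable.** A reader might infer that the arms are no longer comparable. Nothing in the documents shows that starts will differ, and with equal starts of similar patients there is no bias.
- **The size is assumed and may be small.** With 104 and 98 patients and SD 5 h the SE is about 0.70 h, so −0.22 h/day is about 0.3 SE. The figures are simple weighted means. The planned mixed model draws period contrasts partly from within-patient change, so the interaction may be distorted less than raw means suggest. Neither that nor the LTOT repeat has been quantified.
- **The population is deliberate and consistent.** New users are of interest, since the programme teaches oxygen use. That justifies describing them; it does not make a pooled test a randomised comparison. A baseline-only analysis may be in the statistical analysis plan, which was not available here; the protocol specifies none.

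**Conclusion.** The point holds as a low-cost improvement. Every planned between-arm compliance analysis, whether of hours per day, of use minus prescription, or of their LTOT repeats, admits patients after open randomisation and so lacks its protection. Bias follows only if oxygen starts differ between arms in number or type of patient. On assumed inputs the shift in mean use is 0 with like starts, 0.06 to 0.22 h/day under moderate differences, and up to about 1.1 h/day (rejection rate 27% instead of 5%) at the extreme. The direction and size in this trial cannot be derived from the protocol. A reader might also infer that the trial's main result is compromised. It is not: compliance is a secondary, exploratory criterion, and the hospital-days analysis does not use this subgroup.

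**What to change.** In section 7.B.3.5, make the main between-arm compliance analysis, for both hours per day and use minus prescription, in patients on oxygen therapy at Selection. Make the LTOT repeat in patients prescribed 15 h/day or more at Selection. Section 7.B.3.2 already describes both groups at Selection, and section 7.B.3.7 already uses an oxygen-at-Selection subgroup for pulse rate and SpO2. Describe patients who start oxygen or LTOT after Selection separately by arm without a test, or keep the at-any-time population as a descriptive supplement. Align the population wording in section 6.A.2.8.

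**Cost.** Wording only, on the same *NOWOX* data. Later starters leave the tested comparison. The new population is a genuine baseline subgroup but not an exact randomisation stratum, because the stratification factor in section 3.A, "need for respiratory assistance", combines oxygen and Non-Invasive Ventilation. The change does not deal with dropout or with patients who stop oxygen during follow-up.

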  - ✓ Results and date of the most recent pulmonary function tests available (*including Forced Expiratory Volume in 1 second (FEV1) and Forced Vital Capacity (FVC), as both raw values and percentages of predicted values, as well as FEV1/FVC ratio*), performed in stable state less than one year prior to Visit 0,
  - ✓ Patient-reported number of previous moderate and severe COPD exacerbations (*as defined in section 6.A.2.2*) having occurred in the year prior to Visit 0,
- Medical and surgical history not related to COPD and concomitant diseases,
- COPD and non-COPD medication, including oxygen therapy, CPAP, Non-Invasive Ventilation and vaccines performed in the year prior to Visit 0 (*see section 5.D*), and contraception method used, if applicable,
- Start date and criteria for oxygen prescription, if applicable:
  - ✓ Results and date of the most recent resting arterial or capillary blood gases on room air available, performed in stable state (*defined by a period of at least 3 weeks without exacerbation*), within 12 months prior to Visit 0 (*including pH, PaO2, PaCO2, HCO3 and SaO2*),

- ✓ Presence/absence of the following (*including dates of measurement or assessment, when present*): pulmonary hypertension, peripheral oedema and haematocrit > 55%.

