## VISIT AT THE INVESTIGATIONAL CENTRE (*VISIT 1*)

Before seeing the investigator, patients will complete on their own **the three (3) following questionnaires** (*as detailed in section 6.A.2.4 and 6.A.2.7 and provided in Appendix 3*):

- The COPD-specific version of the St George's Respiratory Questionnaire (*SGRQ-C*),
- The 15D health-related quality of life instrument (*available from: <http://www.15d-instrument.net>*),
- The Hospital Anxiety and Depression Scale (HADS).

Validated versions of these three (3) questionnaires in the four (4) study languages (*German, French, Italian and Spanish*) will be used.

**During Visit 1**, the investigator will record the following data in the e-CRF:

- Date of Visit 1,

- Results of the physical examination including vital signs (*i.e.*, *systolic and diastolic blood pressures*), weight and pulse oximetry (*pulse rate and SpO2*) on room air and also on oxygen for patients on oxygen therapy,
- Changes in social conditions, if applicable,
- Changes in smoking status, if applicable,
- Recovery from concomitant diseases since Visit 0, if applicable,
- Assessment of the severity of dyspnoea using the modified Medical Research Council Dyspnoea Scale ,
- Comorbidities to allow the calculation of the Charlson Comorbidity Index ,
- Changes in COPD and non-COPD medication, including oxygen therapy, CPAP, Non-Invasive Ventilation and vaccines (*as detailed in section 5.D*), since Visit 0, if applicable,
- Occurrence of COPD exacerbations (*as defined in section 6.A.2.2*) since Visit 0,
- Occurrence of other Adverse Events (*see section 6.B*) since Visit 0,
- Results and dates of the medical evaluations and laboratory samplings performed during the *Run-In Period*,
- Serial number of the *NOWOX* device assigned to the patient, if applicable.

**At the end of the visit**, if the patient is on oxygen therapy, the investigator will give to the patient the *NOWOX* medical device, after having initialised it and having explained to the patient its correct use (*see section 5.A.4.1*). All patients on oxygen therapy will receive the *NOWOX* user manual and simplified user sheet in their native language and they will be instructed to wear the *NOWOX* each time they use oxygen therapy and to bring it at each of their study visits at the investigational centre.

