## 5.D CONCOMITANT TREATMENTS

All concomitant treatments administered to the patient (*including vaccines, oxygen therapy, home ventilation and CPAP*) will be recorded by the investigators in the e-CRF, with the following information:

- **For the pharmaceutical therapies:** treatment names and dosage, route of administration, dose per administration and posology, start and end dates or ongoing medication, and the reason for their prescription,
- **For the vaccines:** names and date of administration,
- **For oxygen therapy:** start and, if applicable, end dates, daily prescribed hours of use, prescribed flow rates (*at rest, during exercise and during sleep*), type of oxygen source(s) including the name of the device(s) used,
- **For home ventilation and CPAP:** start and end dates, if applicable.

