#### 7.B.3.2. Description at Selection and during the Run-In Period

At Selection (*Visit 0*) and during the *Run-In Period (up to the end of Visit 1)*,

- patients' background, demographic data, social conditions,
- characteristics of the study disease, (*including GOLD stages classification and combined severity assessment classes as defined in section 3. separately*),
- need for oxygen therapy at Selection (*whatever its duration prescribed*) with its criteria for prescription and average daily duration prescribed,
- need for continuous Long Term Oxygen Therapy (*i.e., with daily oxygen duration prescribed of 15 hours or more*) at Selection,
- need for home Non-Invasive Ventilation (NIV) at Selection with its average daily duration prescribed,
- need for Continuous Positive Airway Pressure (CPAP) at Selection,
- smoking status and history,
- results of arterial or capillary blood gases,
- vital signs and pulse oximetry (*split by conditions of measurement: either on room air or on oxygen*) measurements,
- as well as the 6-minute walking distance and related parameters (*split by conditions of assessment: either on room air or on oxygen*),
- the patient's self-evaluations, the severity of dyspnoea,
- the Charlson Comorbidity Index score,
- the transthoracic Doppler echocardiography measurements,

- the clinical interpretation of a 12-lead ECG tracing,
- and the modalities of oxygen prescription, if applicable,

will be described by study group (*and globally*), on the Intention To Treat (ITT) data set (*defined in section 7.B.3.1*).

If a secondary PP data set is defined (*see section 7.B.3.1*) and if 10.0% or more of patients from the ITT data set are excluded from the PP data set, the description of patients by study group (*and globally*) at Selection and during the *Run-In Period (up to the end of Visit 1)* will be repeated on the PP data set, for all parameters apart from standard safety evaluation criteria.

At Visit 1, CRP, as well as haematology results will be tabulated by study group (*and globally*) as both quantitative parameters (*raw values converted in international units, if necessary*) and qualitative parameters (*relative positions regarding normal ranges in use in each laboratory involved*).

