**SGRQ-C total score and component subscores:** quantitative descriptive statistics of the SGRQ-C total score and of each of its three (3) component subscores (*symptoms, activity and impacts*) will be tabulated by study group and visit, using the observed case approach. The absolute variations "*post-Run-In Period – baseline (self-evaluated prior to Visit 1)*" will also be tabulated by study group and visit, for each score and subscore separately.

Moreover, to visualise the evolution of each score and subscore separately, arithmetic means of each score and their 95.0% confidence intervals will be represented graphically (*the x-axis being the assessment time-axis and the y-axis being the arithmetic mean-axis*) with both study groups being represented separately on the same graph, using the observed case approach.

An analysis over time of the mean profile of the SGRQ-C total score and of each of its subscores separately will be performed within a mixed model to deal with patients followed-up over different duration, using the MIXED procedure of the current version of the SAS® software and type III sums of squares. The global parametric analysis of covariance model on repeated measurements used will include the following factors:

- score assessed during the *Run-In Period* as covariate,
- study group and visit as fixed factors,
- interaction between study group and visit and interaction between study group and score assessed during the *Run-In Period (i.e., the covariate)* as fixed factors,
- patient as random factor.

In a first step, the best structure of the variance-covariance matrix will be identified using the Akaike's Information Criterion (AIC), which is based on the Restricted Maximum Likelihood (REML) and the number of covariance parameters. The model with the AIC lowest value will be considered as the best one. In a second step, inference will be drawn about fixed effects in the frame of the model with the best structure of the variance-covariance matrix selected in the first step.

When relevant, appropriate contrasts will be calculated and the associated confidence intervals will be displayed. In case of a statistically significant interaction evidenced at level  $\alpha = 0.10$ , further separate parametric analyses of variance may be carried out, if appropriate and potentially relevant from a clinical point of view.

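### The mixed models for daily, night and day oxygen use omit a baseline covariate the trial already collects: prescribed daily hours at Selection, for patients then on oxygen

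*Protocol*

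**What the plan says.** **The model.** In section 7.B.3.5, Compliance to oxygen therapy, average daily use over 24 hours and its night and day parts are compared between arms in a mixed model: "The global parametric analysis of variance model on repeated measurements used will include the following factors". The terms are study group and period as fixed factors, "interaction between the study group and the period of evaluation as fixed factor", and patient as random factor. The weekly means before and after each centre visit are analysed in the same way.

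**The population.** The analysis is done "In the subgroup of patients on oxygen therapy at Selection and/or during their study participation", so it includes patients who start oxygen after Selection.

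**The baseline value.** At Visit 0 (section 4.B.1.2) the investigator records "COPD and non-COPD medication, including oxygen therapy, CPAP, Non-Invasive Ventilation and vaccines performed in the year prior to Visit 0", with a reference to section 5.D. Section 5.D lists, for oxygen, "daily prescribed hours of use, prescribed flow rates" among the items. Section 7.B.3.2 describes oxygen need at Selection by arm, "with its criteria for prescription and average daily duration prescribed".

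**Neighbouring analyses.** For SGRQ-C the wording is "The global parametric analysis of covariance model on repeated measurements used will include the following factors", with the Run-In score as covariate. 15D and HADS follow that model. The spirometry, 6MWD, echocardiography and BODE models also adjust for the Run-In value. For oxygen, section 7.B.3.5 further applies the oxygen-use model to relative and absolute differences between 24-hour use and the prescription in force. It also repeats the analyses in patients prescribed 15 hours or more.

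**Status.** Section 7.B makes everything other than the primary analysis exploratory and descriptive, with two-sided tests at 5%.

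**The concern.** Hours used can be expected to depend to some degree on hours prescribed. If so, part of the patient-to-patient spread in use can be explained by a value fixed before the study could influence it. Left out of the model, that spread stays in the error term: the interval for the arm difference is wider than it need be, and a chance imbalance in prescribed hours passes into the estimate. Stratification does not remove this. It uses need for respiratory assistance (oxygen or NIV) as a yes/no factor, not the number of hours.

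Oxygen compliance is a named secondary criterion to which section 1.C promises particular attention, and it is assessed in only part of the 306 patients. What is at stake is the precision of that comparison. The primary analysis and the sample size are not affected.

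**Working it through.** **1. The plan's own figure.** The protocol sizes the trial only for hospital days. Noether's formula for the rank-sum test with p = Φ(10/(25√2)), rounded to 0.611, gives n = (1.960 + 1.282)² / [6 × (0.611 − 0.5)²] = 142.1, so 143 per group. Then 143/(1 − 0.0625) = 152.5, so 153 per group and 306 in all. The figure reproduces, but it says nothing about oxygen use, for which no sample size or power is given.

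**2. Is there a usable baseline value?**
- A device baseline of the outcome does not exist. It is only at the end of Visit 1, after randomisation, that "if the patient is on oxygen therapy, the investigator will give to the patient the" NOWOX device.
- Prescribed hours at Selection do exist for patients then on oxygen (sections 4.B.1.2 and 5.D).
- Patients who start oxygen later have no such value.

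**3. What would the covariate gain?** With correlation r between hours prescribed at Selection and hours used, adjustment multiplies the between-patient variance by 1 − r². Assumptions, none of them in the protocol: 60 oxygen patients per arm (40 as a variant), SD of daily use 5 h, true difference 2 h/day, every analysed patient having the value, one average per patient, two-sample t-test at two-sided 5%. Residual SD = 5√(1 − r²); standardised effect = 2 / residual SD.

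| r | 1 − r² | Residual SD (h) | Effect | Power, 60/arm | Power, 40/arm |
|---|---|---|---|---|---|
| 0 | 1.00 | 5.00 | 0.400 | 58% | 42% |
| 0.1 | 0.99 | 4.97 | 0.402 | 59% | 43% |
| 0.3 | 0.91 | 4.77 | 0.419 | 63% | 46% |
| 0.5 | 0.75 | 4.33 | 0.462 | 71% | 53% |
| 0.7 | 0.51 | 3.57 | 0.560 | 86% | 70% |

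**4. Allowing for patients without a Visit 0 value.** If a share m of analysed patients has the value, the variance factor becomes 1/[m/(1 − r²) + (1 − m)]. With m = 0.75 (assumed) it is 0.93, 0.80 and 0.58 at r = 0.3, 0.5 and 0.7, against 0.91, 0.75 and 0.51 with m = 1. The gain shrinks somewhat but remains.

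**5. Do the use-minus-prescription models already do this?** A difference score has variance factor 1 + k² − 2rk, where k = SD(prescribed)/SD(used). Here r and k are assumed to be the same for the prescription in force as for the one at Selection.

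| r | Covariate | Difference, k = 0.5 | k = 0.75 | k = 1 |
|---|---|---|---|---|
| 0.1 | 0.99 | 1.15 | 1.41 | 1.80 |
| 0.3 | 0.91 | 0.95 | 1.11 | 1.40 |
| 0.5 | 0.75 | 0.75 | 0.81 | 1.00 |
| 0.7 | 0.51 | 0.55 | 0.51 | 0.60 |

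At r = 0.7 the absolute difference recovers most or all of the gain. At r = 0.3 or below it recovers little, or is noisier than no adjustment at all. The fitted slope is not worse anywhere in the table.

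**The case against.** The case for leaving the model as it is has real weight.

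- **The other models are not a like-for-like precedent.** They adjust for the same outcome measured in Run-In. No such measurement exists for device-recorded use, so an analysis of variance here follows from the available data and is not an inconsistency. This stands: the point is a missed improvement, not a contradiction.
- **Prescription already enters a between-arm comparison.** This stands in part. The difference models force a slope of 1. They use the prescription during Follow-Up, which unblinded investigators may change at their discretion (sections 4.B.2 and 5.A.3). They also cover only 24-hour use between visits, so the night, day and weekly models have no counterpart that takes account of prescription. The repeat in patients prescribed 15 hours or more at any time restricts the range of prescriptions but adjusts for nothing.
- **The benefit is not documented.** This stands. A reader might infer that most of the spread in use is spread in prescription, since section 7.B.3.2 describes oxygen whatever its prescribed duration. The protocol gives no distribution of prescribed hours and no correlation. The treatment definitions in section 3 call for at least 15 hours a day of long-term oxygen, so prescriptions may cluster. Section 1.C says use generally falls short of prescription, which makes adherence a separate source of spread.
- **The analysis is exploratory, with no power target**, and baseline prescribed hours are tabulated by arm, so an imbalance would be visible. This also stands and limits the importance of the point.

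A reader might also infer that every analysed patient has a prescription recorded before randomisation. That is not so, because patients who start oxygen after Selection are in the model.

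**Conclusion.** The point holds as a minor efficiency improvement. The oxygen-use models, including the weekly ones, have no baseline covariate, although a suitable value is collected at Visit 0 for patients then on oxygen. Omitting it does not bias the arm contrast; it may widen the interval.

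Under the stated assumptions (60 per arm, SD 5 h, 2 h difference), power rises from about 58% to between 59% and 86% as the correlation goes from 0.1 to 0.7. The gain is at most about 4 points for a correlation up to 0.3, and about 28 points at 0.7. The true position in that range cannot be read from the protocol. The calculation is for 24-hour use; none was made for the night component, which cannot exceed 8 hours.

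The documents do not support reading this as a bias, as an internal contradiction, or as a weakness of the primary result.

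**What to change.** In the mixed model for daily, night and day oxygen use, and in the pre- and post-visit weekly models, add two fixed terms:

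1. prescribed daily oxygen hours at Selection, centred at the mean of the patients on oxygen at Selection;
2. an indicator of being on oxygen at Selection, with the hours term set to 0 for patients who start oxygen later.

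No group-by-covariate interaction is needed. Keep the use-minus-prescription analyses as planned, since they address a different question: use relative to the prescription in force.

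The cost is two model terms and a sentence in the analysis plan. The values are already in the e-CRF, so no extra data, visits or patients are required.
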